3.2 Exclusion Criteria

- 3.2.1 Participants with brain metastases due to confounding effects on the study objectives.
- 3.2.2 History of allergic reactions attributed to compounds of similar chemical or biologic composition to perampanel.
- 3.2.3 Participants receiving any medications or substances that are moderate or strong inducers of CYP3A4 are ineligible. Because the lists of these agents are constantly changing, it is important to regularly consult a frequently-updated medical reference. As part of the enrollment/informed consent procedures, the participant will be counseled on the risk of interactions with other agents, and what to do if new medications need to be prescribed or if the participant is considering a new over-the-counter medicine or herbal product.
- 3.2.4 Participants with uncontrolled intercurrent illness.
- 3.2.5 Participants with psychiatric illness/social situations that would limit compliance with study requirements.

- 3.2.6 Pregnant women are excluded from this study because perampanel is an anti-seizure agent with the potential for teratogenic or abortifacient effects. Because there is an unknown but potential risk for adverse events in nursing infants secondary to treatment of the mother with perampanel, breastfeeding should be discontinued if the mother is treated with perampanel.
- 3.2.7 Participants with a history of suicide attempt or current active suicidal ideation with intent as defined by Columbia Suicide Severity Rating Scale (C-SSRS) type 4-5, due to the potential for suicidal ideation with the use of all anti-seizure medications.
- 3.2.8 Participants who are unable to swallow pills.
- 3.2.9 Participants with tumor associated seizures greater than one month before planned surgery.
- 3.2.10 Participants currently receiving treatment with more than one anti-seizure medication.

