5. TREATMENT PLAN

5.1. Treatment Regimen

Perampanel will be given every day until meeting the study endpoint(s). Reported adverse events and potential risks are described in Section 7. Appropriate dose modifications are described in Section 6. Other anti-seizure medication(s) may be administered during perampanel maintenance therapy as clinically indicated.

Cohort 1

Participants who are already receiving an anti-seizure medication pre-operatively for treatment of tumor-associated seizures will receive their last dose at least 36 hours before scheduled surgery start-time, and then will be switched to perampanel. The loading dose of perampanel will be 6mg by mouth, given on the day prior to surgery (12-36 hours before scheduled start time), followed by a maintenance dose of 4mg by mouth once a day. Participants will be requested to maintain a drug diary of each dose of medication. The drug diary will be returned to clinic staff at the end of each month.

Study day	Perampanel dose
Day 1 (load)	6mg
Day 2+ (maintenance)	4mg

Cohort 2

Perioperative and post-operative seizure management will be performed by the primary treating physician(s) according to institutional standards.

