5.5. Criteria for Taking a Participant Off Protocol Therapy

Duration of therapy will depend on individual response, evidence of disease progression and tolerance. In the absence of treatment delays due to adverse event(s), treatment may continue for 12 months or until one of the following criteria applies:

- Intercurrent illness that prevents further administration of treatment
- Unacceptable adverse event(s)
- Participant demonstrates an inability or unwillingness to comply with the oral medication regimen and/or documentation requirements
- Participant decides to withdraw from the protocol therapy
- General or specific changes in the participant's condition render the participant unacceptable for further treatment in the judgment of the treating investigator

Participants will be removed from the study protocol when any of these criteria apply. The reason for removal from protocol, and the date the participant was removed, must be documented in the case report form (CRF). Alternative care options will be discussed with the participant. Perampanel may be continued on a clinical basis by the primary treating physician. If the participant is taken off protocol for active suicidal ideation with intent (defined by the Columbia Suicide Severity Rating Scale Type 4-5), the Principal Investigator will arrange for immediate psychiatric evaluation.

When a participant is removed from protocol therapy and/or is off of the study, the participant's status must be updated in OnCore in accordance with [REGIST-OP-1](#).

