7.3. Adverse Event Reporting

7.3.1. In the event of an unanticipated problem or life-threatening complications treating investigators must immediately notify the Overall PI.

7.3.2. Investigators **must** report to the Overall PI any adverse event (AE) that occurs after the initial dose of study treatment, during treatment, or within 30 days of the last dose of treatment on the local institutional SAE form.

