10. STUDY CALENDAR

Baseline evaluations are to be conducted within 2 weeks prior to start of protocol therapy. Scans must be done ≤ 2 weeks prior to the start of therapy. If the participant's condition is deteriorating, laboratory evaluations should be repeated within 48 hours of assessment. Study visits will be performed at monthly intervals by clinic or phone interviews. Clinical response will be evaluated at each study visit. Adverse events will be assessed with each study visit at minimum, and more frequently as clinically indicated.

	Baseline	Pre-surgery	During surgery	Post-surgery maintenance	Off Study ^d
Perampanel administration (Cohort 1)		A		Every day	
Electrocorticography			X		
Tumor biopsy			X		
Informed consent	X				
Demographics	X				
Medical history	X				
Concurrent Medications	X-----X				
Physical exam	X				
Vital signs	X				
Height	X				
Weight	X				
Performance status	X			Every month	
B-HCG	X ^b				
Serum chemistry ^a	X				
Seizure Frequency	X			Every month	
Tumor Measurements	X			X ^c	
Radiologic Evaluation	X			X ^c	
Adverse Event Evaluation		X-----X ^e			

A: Perampanel: Dose as assigned
 
a: Albumin, alkaline phosphatase, total bilirubin, bicarbonate, BUN, calcium, chloride, creatinine, glucose, LDH, phosphorus, potassium, total protein, SGOT [AST], SGPT [ALT], sodium.
 
b: Serum pregnancy test (women of childbearing potential).
 
c: At discretion of primary treating neuro-oncologist.
 
d: Perampanel may be continued on a clinical basis off protocol.
 
e: Adverse events will be evaluated up to 30 days after study completion.
					

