13.4. Interim Monitoring Plan

All participants will undergo continuous safety monitoring.

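### The plan defines its psychiatric referral by C-SSRS type 4-5, but schedules no suicidality screen during up to 12 months of perampanel and does not list that finding as a reason to stop therapy

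*Combined protocol and SAP*

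**What the plan says.** Section 3.2.7 excludes anyone who has attempted suicide in the past, and anyone with "current active suicidal ideation with intent as defined by Columbia Suicide Severity Rating Scale (C-SSRS) type 4-5". The reason given is "due to the potential for suicidal ideation with the use of all anti-seizure medications".

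Section 5.5 lists five grounds for ending protocol therapy. In short, they are another illness that prevents treatment, an intolerable adverse event, non-compliance, the participant's own decision, and a change in condition judged by the treating investigator. Suicidal ideation is not named among them. A later sentence deals with a participant "taken off protocol for active suicidal ideation with intent (defined by the Columbia Suicide Severity Rating Scale Type 4-5", and requires the Principal Investigator to arrange psychiatric evaluation at once.

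Cohort 1 takes perampanel daily until progression or for at most 12 months (sections 1 and 5.5), at up to 8 mg a day (section 6). Section 10 sets the contacts: "Study visits will be performed at monthly intervals by clinic or phone interviews". It adds: "Adverse events will be assessed with each study visit at minimum, and more frequently as clinically indicated". The two measures that the calendar marks as monthly are performance status and seizure frequency.

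Other safety provisions also apply. Under 7.3.2 investigators must "report to the Overall PI any adverse event (AE) that occurs after the initial dose of study treatment", up to 30 days after the last dose. Under 12.2 the safety monitoring committee reviews toxicity up to four times a year. Section 13.4 states: "All participants will undergo continuous safety monitoring".

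**The concern.** The protocol names the risk, chooses an instrument and sets an action level, but no step during treatment produces a result on that instrument. The 5.5 sentence is also conditional. It says what follows once a participant has been removed for such ideation, and does not say that such ideation requires removal. If the plan is followed to the letter, someone who develops type 4-5 ideation in month 4, say, is found only if the ideation is volunteered or happens to come up in general adverse event questioning, possibly by phone. The list of likely adverse events in 7.1.1 does not include ideation, so it does not prompt staff to ask.

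What is at stake is the safety of Cohort 1: ideation may be missed, or the referral delayed.

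**Working it through.** The plan gives no figure to reproduce. The check sets the sections side by side and then counts the work that a screen would add.

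**Where the scale appears.** In the text available, the C-SSRS is mentioned only in 3.2.7 and 5.5. Both use it to define a degree of ideation, and neither says when or by whom it is given. Appendix C was not available to read, but the contents list gives its subject as drug interactions, so a visit schedule there is unlikely.

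**What the calendar schedules (section 10).**
- Rows: 18. Footnotes: 6 (A, and a to e).
- Rows or footnotes for the C-SSRS or any other suicidality, mood or psychiatric screen: 0. The introductory text of the section has none either.
- After surgery: two named monthly measures, plus general adverse event evaluation at every visit, which runs on to 30 days after study completion.

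**From finding to action (5.5).**
- Step 1, ideation is detected: no scheduled screen, general adverse event review only.
- Step 2, it is graded by C-SSRS type: no step assigned.
- Step 3, the participant is removed: possible under the intolerable adverse event or investigator judgment grounds, but not required for type 4-5.
- Step 4, psychiatric evaluation: required, but worded to follow from step 3.

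The plan makes step 4 firm and leaves steps 1 to 3 open.

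**Baseline is different.** Section 3.2.7 applies type 4-5 at entry, and section 4.1 (general guidelines) has an investigator confirm eligibility and the study team complete a checklist. The calendar also has no row for other entry checks: blood counts (3.1.5), viral loads (3.1.6 to 3.1.8) or cardiac class (3.1.10). A missing baseline row therefore says little about whether the check is made.

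**Size of the added work.** Inputs are 10 participants in Cohort 1 (13.1), at most 12 monthly contacts each (sections 1 and 10), and an assumed 5 minutes per administration, with a range of 3 to 10.
- Ceiling: 10 × 12 = 120 administrations.
- Hours: 120 × 5 / 60 = 10; at 3 minutes, 120 × 3 / 60 = 6; at 10 minutes, 120 × 10 / 60 = 20.
- If mean time on study is an assumed 6 months, because participants leave at progression: 10 × 6 = 60 administrations, or 60 × 5 / 60 = 5 hours (3 to 10).
- Optional extra, a recorded entry result for all 20 participants: 120 + 20 = 140 administrations, or 11.7 hours (7.0 to 23.3).
- Optional extra, Cohort 2 also screened monthly: 140 + 10 × 12 = 260 administrations, or 21.7 hours (13.0 to 43.3).

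**The case against.** The strongest reply is that no promised assessment is broken. Both sections use the scale as a definition, and neither commits to giving it repeatedly. A clinician can apply the definition whenever ideation comes to light. Adverse events are reviewed at least monthly, reported to the Overall PI and seen by the safety monitoring committee. Section 6 lets the drug be stopped at once for a serious event attributed to it. Section 3.2.7 also keeps out people with a past attempt, and 3.2.5 excludes psychiatric illness that would limit compliance. Cohort 1 is at most 10 people on a marketed drug.

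Much of this stands. A reader might infer that participants enter unscreened. The documents do not support that, because 3.2.7 and the eligibility checklist imply a check at entry. A reader might also infer that suicidality goes unmonitored on treatment. That is too strong as well, since general adverse event review is a real, at least monthly, safeguard. Nor do the documents show that the protocol breaks its own rule.

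What the reply does not cover is the period on treatment. General review asks no set question about suicidality and yields no C-SSRS type, and the removal grounds in 5.5 help only after ideation has been found. A C-SSRS is also a form of asking, at the same contacts, but it makes sure that the question is put every time and graded on the scale that 5.5 uses.

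**Conclusion.** The point holds for the treatment period. The plan has a referral defined by C-SSRS type 4-5, no scheduled step that produces a type, and no rule that such a finding ends protocol therapy. The exposure is at most 10 participants and 120 monthly contacts, or 60 contacts at an assumed mean of 6 months on study. All of these contacts have general adverse event review, and none has a scheduled suicidality screen. These figures measure the gap in the schedule and do not measure harm. With no incidence in the documents, they should not be read as a number of cases that would be missed.

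The missing baseline row is minor. It would also be a misreading to say that 5.5 already removes a participant for type 4-5 ideation: it only refers one who has been removed for it.

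This is a low-cost safety improvement that the sponsor should make. Sample size, power and the primary comparison are untouched. The conclusion assumes that no form outside these documents schedules the scale; the eligibility checklist and case report forms were not available to check.

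**What to change.** - Add a C-SSRS row to the section 10 calendar for Cohort 1, at each existing monthly clinic or phone contact while on perampanel, and record the type on the case report form.
- Amend 5.5 so that a type 4-5 result is itself an off-therapy criterion and triggers the immediate psychiatric evaluation.
- Write a short procedure for a positive screen by phone: who is called, how soon, and who stays in contact with the participant meanwhile.
- Optional: record the entry C-SSRS that 3.2.7 implies.
- Optional: screen Cohort 2 on the same schedule. Its care is left to usual practice ("Perioperative and post-operative seizure management will be performed by the primary treating physician(s) according to institutional standards"), but 3.2.7 attributes the risk to every drug of this class, so those taking one share it.

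The cost is a calendar, case report form and 5.5 amendment, plus about 10 staff hours at the ceiling (6 to 20). Per participant that is 12 × 5 = 60 minutes over a year (36 to 120). No extra visit or invasive procedure is needed. The downsides are the staff time, the phone procedure, and unequal ascertainment if only Cohort 1 is screened. In that case rates of ideation should not be compared between cohorts.

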5.6. Duration of Follow Up

Participants will be followed as clinically indicated after removal from protocol or until death, whichever occurs first. Participants removed from protocol therapy for unacceptable adverse event(s) will be followed until resolution or stabilization of the adverse event. After completion of the study, if the treating neurologist cannot be contacted or the participant no longer wishes to see their treating neurologist, the principal investigator will help the participant to transition care to a different treating neurologist and will follow them clinically until then.

5.7. Criteria for Taking a Participant Off Study

Participants will be removed from study when any of the following criteria apply:

- Disease progression
- Lost to follow-up
- Withdrawal of consent for data submission
- Death

The reason for taking a participant off study, and the date the participant was removed, must be documented in the case report form (CRF). In addition, the study team will ensure the participant's status is updated in OnCore in accordance with [REGIST-OP-1](#).

6. DOSING DELAYS/DOSE MODIFICATIONS

Perampanel dose modifications are permitted as clinically indicated to optimize seizure control and minimize adverse effects. Dose adjustment may be performed by the primary treating neurologist and/or study investigators. For any adjustment, the Principal Investigator, [name], will be notified. A maximum daily maintenance dose for this study will be 8mg.

At the completion of the study, if perampanel is not clinically indicated and/or planned to be withdrawn, the daily dose will be tapered down by 2mg per week to the minimum therapeutic dose of 4mg, then stopped. If perampanel is being discontinued for lack of seizure efficacy, an alternative anti-seizure medication chosen at the discretion of the primary treating neurologist will be started and titrated to a therapeutic dose, after which perampanel will be tapered off as above. If the participant experiences a serious adverse event attributed to perampanel, the drug may be stopped immediately if, at discretion of the Principal Investigator, the benefits outweigh the risks.

7. ADVERSE EVENTS: LIST AND REPORTING REQUIREMENTS

Adverse event (AE) monitoring and reporting is a routine part of every clinical trial. The following list of reported and/or potential AEs (Section 7.1) and the characteristics of an observed AE (Section 7.2) will determine whether the event requires expedited reporting **in addition** to routine reporting.

7.1. Adverse Event List

7.1.1. Adverse Event List for Perampanel

Based on pooled adverse events seen in $\geq 2\%$ of patients and more frequently than placebo in controlled trials of perampanel at a dose of 4mg for drug-resistant focal epilepsy (N=172),¹⁶ the most likely adverse events to be seen in this study include:

- dizziness
- somnolence
- irritability
- fatigue
- vertigo
- anxiety
- weight gain
- oropharyngeal pain

Participants will be referred to the package insert(s) for the comprehensive list of

adverse events.

7.2. Adverse Event Characteristics

- **CTCAE term (AE description) and grade:** The descriptions and grading scales found in the revised NCI Common Terminology Criteria for Adverse Events (CTCAE) version 5.0 will be utilized for AE reporting. All appropriate treatment areas should have access to a copy of the CTCAE version 5.0. A copy of the CTCAE version 5.0 can be downloaded from the CTEP web site http://ctep.cancer.gov/protocolDevelopment/electronic_applications/ctc.htm.
- **For expedited reporting purposes only:**
 - AEs for the agent(s) that are listed above should be reported only if the adverse event varies in nature, intensity or frequency from the expected toxicity information which is provided.
 - Other AEs for the protocol that do not require expedited reporting are outlined in the next section (Expedited Adverse Event Reporting) under the sub-heading of Protocol-Specific Expedited Adverse Event Reporting Exclusions.
- **Attribution** of the AE:
 - Definite – The AE *is clearly related* to the study treatment.
 - Probable – The AE *is likely related* to the study treatment.
 - Possible – The AE *may be related* to the study treatment.
 - Unlikely – The AE *is doubtfully related* to the study treatment.
 - Unrelated – The AE *is clearly NOT related* to the study treatment.

7.3. Adverse Event Reporting

7.3.1. In the event of an unanticipated problem or life-threatening complications treating investigators must immediately notify the Overall PI.

7.3.2. Investigators **must** report to the Overall PI any adverse event (AE) that occurs after the initial dose of study treatment, during treatment, or within 30 days of the last dose of treatment on the local institutional SAE form.

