4.1 General Guidelines for DF/HCC Institutions

Institutions will register eligible participants in the Clinical Trials Management System (CTMS) OnCore. Registrations must occur prior to the initiation of any protocol-specific therapy or intervention. Any participant not registered to the protocol before protocol-specific therapy or intervention begins will be considered ineligible and registration will be denied.

An investigator will confirm eligibility criteria and a member of the study team will complete the protocol-specific eligibility checklist.

Following registration, participants may begin protocol-specific therapy and/or intervention.

Issues that would cause treatment delays should be discussed with the Overall Principal Investigator (PI). If the subject does not receive protocol therapy following registration, the subject must be taken off study in the CTMS (OnCore) with an appropriate date and reason entered.

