13.7. Reporting and Exclusions

13.7.1. Evaluation of Toxicity

All participants will be evaluable for toxicity from the time of their first treatment.

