13.7.2. Evaluation of the Primary Efficacy Endpoint

All participants in Cohort 1 who receive at least one dose of study treatment and all participants in Cohort 2 will be evaluable for response.

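### The protocol's AE start points disagree, so events between the protocol-directed stop of a Cohort 1 participant's anti-seizure drug and the perampanel load are not assured of capture

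*Combined protocol and SAP*

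**What the plan says.** Section 5.1 directs that Cohort 1 participants already treated for tumor-associated seizures "will receive their last dose at least 36 hours before scheduled surgery start-time, and then will be switched to perampanel". The perampanel load is due 12 to 36 h before the scheduled start of surgery, and the dosing table labels the load as Day 1.

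Section 4.1 (General Guidelines) places this switch on study: "Registrations must occur prior to the initiation of any protocol-specific therapy or intervention". It also states: "If the subject does not receive protocol therapy following registration, the subject must be taken off study", with a date and reason entered.

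The documents give the start of safety collection in several places:

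- Section 7.3.2 requires investigators to report to the Overall PI "any adverse event (AE) that occurs after the initial dose of study treatment".
- Section 13.7.1 states: "All participants will be evaluable for toxicity from the time of their first treatment".
- Section 7.3.1 requires immediate notification of unanticipated problems and life-threatening complications, with no dose condition.
- Section 7.5 requires all AEs on the toxicity case report forms, with no start point.
- In the Section 10 calendar, as extracted, the AE row is blank at Baseline and first marked under Pre-surgery. The perampanel load sits in that same column.

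Section 11.2 defines baseline seizure frequency from the month before surgery and measures time to seizure recurrence from the date of surgery.

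**The concern.** For these participants the first act the protocol directs is stopping a drug, and this can come before any study dose. A seizure is the foreseeable harm of that step. The two provisions that name a starting event for safety data both name the first dose or treatment, which can fall after the stop.

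Two other rules add to this. A seizure in the gap falls in the month before surgery, so it would enter the data as baseline seizure frequency with nothing linking it to the switch. Section 7.2 also defines attribution only in relation to study treatment and has no category for withdrawal of the prior drug.

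Section 13.4 promises continuous safety monitoring of all participants, and under Section 12.2 the DSMC reviews toxicity data. Both depend on what is collected. With at most 10 participants in Cohort 1, one event handled differently from one participant to the next is 10% of the cohort (1/10).

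**Working it through.** The plan states no figure on this point, so there is none to reproduce. The check has two parts.

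**Length of the gap.** Inputs, all from Section 5.1: last dose of the prior drug at L hours before surgery, with L at least 36; load at P hours before surgery, with P between 12 and 36. The gap is L − P.

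| L (h before surgery) | P = 36 | P = 24 | P = 12 |
|---|---|---|---|
| 36 (minimum in 5.1) | 0 h | 12 h | 24 h |
| 48 (assumed, for range) | 12 h | 24 h | 36 h |
| 60 (assumed, for range) | 24 h | 36 h | 48 h |

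The gap can be zero in one corner and reaches 24 h at the minimum washout. Because L has no ceiling, neither does the gap.

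**Which provisions reach an event in the gap.** Take a non-life-threatening seizure after the last dose of the prior drug and before the load.

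- 7.3.2: outside, because it precedes the first dose.
- 13.7.1: outside, because it precedes first treatment.
- 7.3.1: reaches it only if it is judged an unanticipated problem or life-threatening.
- 7.3.4: seizure hospitalization is exempt from expedited reporting and goes to the case report form, so capture depends on when routine collection begins.
- 7.5: inside if read literally, but no start time is given, and the form it names is the toxicity form, for which 13.7.1 sets a later start.
- Section 10 calendar: undetermined. The Pre-surgery column does not show whether AE evaluation begins before or after the load. If before, it disagrees with 7.3.2 and 13.7.1. If after, the gap is uncovered.
- 11.2: recorded, but as baseline frequency.

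Two provisions exclude the event, one includes it by silence, one is ambiguous, and one records it under another label.

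**Registered but undosed participants.** Whatever the reason for not dosing, 4.1 requires removal from study with a reason entered. Under 13.7.1 the participant never becomes evaluable for toxicity. The entered reason is an administrative record, not a graded and attributed AE.

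**The case against.** The strongest reply is that the documents do reach the gap. Section 7.5 asks for all AEs, 7.3.1 has no dose condition, the calendar row begins pre-surgery, baseline seizure counts include the gap, and removal from study needs a stated reason. Section 7.3.2 governs only one channel, a report to the Overall PI on the local SAE form. This stands against the stronger inference a reader might draw, that harm in the gap is never reported. It does not remove the inconsistency, because none of these provisions says that AE collection begins at the stop of the prior drug, and 13.7.1 says otherwise for toxicity.

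A reader might also infer that a participant who has a seizure in the gap goes undosed and leaves the study, so that Cohort 1 holds only those who came through the switch. The documents do not support that: no section says such a seizure prevents the load, and Section 5.2 sets no pre-treatment criteria.

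The size can also be overstated. Applying Section 2.1's upper figure of 60% to 10 participants gives 6 (0.60 × 10), but that figure describes seizures in HGG generally. It is not the share of this cohort on a drug before surgery, and exclusions 3.2.9 and 3.2.10 remove some seizure patients. The gap also includes the prior drug's ordinary dosing interval, so it does not measure time without drug effect. Both objections stand.

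Finally, requiring one dose for the primary efficacy set ("All participants in Cohort 1 who receive at least one dose of study treatment", Section 13.7.2) is a defensible choice for a drug effect on intraoperative HFOs. It deletes no safety data and is not at issue.

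**Conclusion.** The point holds as an inconsistency that leaves capture unassured. Sections 7.3.2 and 13.7.1 start at first dose or treatment, 7.5 gives no start, and the calendar can be read either way. A protocol-directed stop of an existing drug can precede all dose-based windows by 0 to 24 h at the minimum washout, and by longer where the last dose is earlier. Events in that interval may be recorded by one reader of the protocol and omitted by another, and a seizure there would be labelled baseline.

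The scope is limited to Cohort 1 participants already on an anti-seizure drug (at most one drug, by exclusion 3.2.10). For other Cohort 1 participants the load is the first step, although the loss of undosed registrants from toxicity evaluability applies to them too. The number affected and the chance of an event cannot be derived from the documents.

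The conclusion rests on reading first treatment in 13.7.1 as the perampanel load, which the Day 1 label in 5.1 supports, and on registration preceding the stop, as 4.1 requires. It implies nothing about the washout or dosing rules.

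**What to change.** 1. In 7.3.2 and 13.7.1, start AE reporting and toxicity evaluability at registration, or at the first protocol-directed change in anti-seizure medication.
2. Give 7.5 the same start point, and annotate the calendar's AE row so that it is clear collection begins before the load.
3. Keep registered but undosed Cohort 1 participants in the safety listing, with the number and the reason. A sentence in 4.1 should say that removal from study does not remove their safety data.
4. List seizures between the last dose of the prior drug and the load separately from baseline seizures.

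The cost is wording in four sections and the calendar, one additional listing, and a few more AE entries over one or two days per participant. The efficacy set, the endpoints and the treatment schedule do not change.
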